2.3 Sample Size

Sample size was calculated based on the primary outcome of time to first successful liberation from mechanical ventilation. The calculation treated death as a censoring event. Sample sizes assuming a hazard ratio ranging between 1.2 to 1.3 were calculated. We used 80% power and a 2-sided type I error of 5%. We also assumed a 5% rate of dropout.

As planned a priori, aggregate blinded data from the first 120 patients was used to re-estimate the sample size. Median time to successful liberation in the entire cohort was 6.8 days. The minimal clinically important difference was deemed to be 1 day. Assuming a hazard ratio of 1.3, to demonstrate a reduction in the median

duration of ventilation by 1.78 days, we will require 529 patients or 558 patients if we assume a loss to followup of 5%. Assuming a hazard ratio of 1.25 will require 770 patients to demonstrate a difference of 1.5 days (Table xx). We expect to enroll a minimum of 558 patients within the planned 5 year of enrollment.

Median Time (PSV)	Median Time (PAV)	Difference	Hazard Ratio	Required Events	Total N	Total N(5% lost)
7.40	6.17	1.23	1.20	944	1095	1153
7.40	5.92	1.48	1.25	630	729	768
7.40	5.69	1.71	1.30	456	526	554
7.50	6.25	1.25	1.20	944	1097	1155
7.50	6.00	1.50	1.25	630	731	770
7.50	5.77	1.73	1.30	456	527	555
7.55	6.29	1.26	1.20	944	1098	1156
7.55	6.04	1.51	1.25	630	731	770
7.55	5.81	1.74	1.30	456	528	556
7.60	6.33	1.27	1.20	944	1098	1157
7.60	6.08	1.52	1.25	630	731	771
7.60	5.85	1.75	1.30	456	528	556
7.70	6.42	1.28	1.20	944	1101	1159
7.70	6.76	1.54	1.25	630	733	772
7.70	5.92	1.78	1.30	456	529	557

2.4 Interim Analyses

No interim analyses of the outcomes will be conducted.

2.5 Timing of outcome assessments

The primary outcome is measured during the participant's initial ICU stay and hospital stay. Secondary outcomes are measured daily during the patients ICU stay, and at time of transfer between ICU and non-ICU hospital beds, at hospital discharge, and at 90 days post randomization.

2.6 Timing of final analysis

All outcomes will be analyzed collectively after the final 90-day follow-up has been completed on the last patient randomized, and the data verification and database locking is complete. Planned analyses identified in the trial protocol and this SAP will be performed only after the last patient has completed the 90 day follow-up assessment visit, the RAVE database has been cleaned and locked, and results from separate analysis for protocol violations and deviations have been completed and declared final. Blinded data review meetings will be held before locking the RAVE database and, again, before declaring final electronic copies of the data in Excel spreadsheets. There will be no un-blinded review and analyses will not commence until the SAP has been approved by the Lead Principal Investigators and Trial Statisticians. Any post-hoc exploratory analyses performed to provide support for planned analyses but not identified in this SAP will be clearly identified as unplanned analyses. All analyses and their interpretation will be conducted independently of the trial funders.

3 Statistical Principles

3.1 Regarding P-Values and Statistical Significance

Controversy continues to exist around the use of p-values and significance testing. The problems are not so much the fault of p-values themselves but arise in the mechanical comparison to an arbitrary threshold of say 0.05 which categorizes results into, "statistically significant" or "not statistically significant." It is in this binary decision that the Type 1 error arises and the risk of making any Type 1 error among all tests increases with the number of tests. It is this problem that leads many to adjust p-values (or equivalently the threshold per test) in analysis.

However, the p-value as it stands simply represents a continuous measurement of the strength of the statistical evidence one has against some hypothesis (no difference between groups in this instance). It is thus best

statistical practice to report for all outcomes analyzed, the estimated treatment effect, the 95% (or some other suitable level) confidence interval (CI) and the p-value. This is the practice that will be adopted in the analysis. This gives a reader all of the necessary information to put the results into proper context. Note that the policy of some journals to request only the CI does not solve the problem it is intended to solve. Specifically, a reader will still mentally make the "significance conclusion" entirely through the CI.

Finally, the ASA statement on p-values [24] recommends all computed p-values be reported to provide sufficient context to evaluate the evidence in totality.

Treatment effect estimates will be reported with their 95% confidence intervals.

3.2 Handling of Incomplete Data

It is important to realize that the problem of incomplete data is distinct from ITT. The ITT philosophy is to attribute the available patient data to the group they were randomized to, irrespective of compliance to randomization. However, it is not possible to analyze data that you do not have. Therefore, we will begin with the complete case analysis. However, this analysis can be biased, although if missing data is minimal, less than 5% say, bias will be minimal and conclusions will not be affected by more sophisticated approaches.

There is controversy regarding the appropriateness of imputing outcome data in clinical trials. Therefore, even if loss to follow-up (i.e. missing outcome) exceeds 5% no imputation methods will be employed for post-randomization outcomes. The main value of imputation techniques is to enable an analysis to use all complete data. Some unpublished simulations developed by the statistician demonstrate that if the outcome is the only thing missing, even if missing at random, multiple imputation has virtually no effect on bias or precision. Furthermore, post-randomization outcome data is frequently not missing at random and other simulations conducted by the statistician show multiple imputation may not correct the bias incurred by data not missing not at random. Also note that since the primary analysis is a time-to-event analysis, no subjects are dropped from the analysis, they are simply censored if necessary. Multiple imputation may be employed to handle missing covariate data in secondary, adjusted analyses.

3.3 Inverse Probability Weighted Analysis

In analyses that do not employ survival analysis methods where there is enough missing outcome data to cause concern for the complete case analysis, an inverse probability weighted analysis will be conducted. This is a two-step process.

First, a logistic regression model (or machine learning model) is fit to the complete ITT sample. The outcome for this model is 1 if the follow-up data (outcome) is present and 0 if missing. A list of baseline variables considered most likely to predict drop-out will be identified and used as covariates in the logistic regression model. The idea here is to obtain a model that predicts well who was complete and who was not. Once the model is fit, it will be used to generate predicted probabilities of "not being missing" for each patient.

The second stage proceeds on the complete case data as before, however the reciprocals of the predicted probabilities from the previous stage are used as regression weights. This weighted analysis attempts to correct for the selection bias that could exist in the complete case analysis.

4 Trial population

The study population eligibility and selection criteria are detailed in the study protocol and summarized briefly below.

4.1 Eligibility Criteria

We will include critically ill adult patients (age \geq 18 years) receiving invasive MV for ARF for at least 24 hours, and judged ready to commence, and be maintained with, partial ventilatory support (tolerating PSV

for at least 30 minutes) (20) but not yet ready for extubation (not yet ready for a spontaneous breathing trial (SBT) or having failed an SBT). The initial screening criteria will include critically ill patients who are:

- A1. Adult patients ≥ 18 years
- A2. Intubated, or tracheostomized, receiving invasive ventilation ≥ 24 hours

And will exclude patients who meet one or more of the following Screening Exclusion Criteria:

- A3. Anticipating withdrawal of life suport and/or shift to palliation
- A4. Severe central neurologic disorder
- A5. Known or suspected severe or progressive neuromuscular disorder
- A6. Severe COPD
- A7. Broncho-pleural fistula
- A8. Tracheostomy present at ICU admission for prolonged MV (>21 days)
- A9. Current enrolment in a confounding study
- A10. Previous randomization in the PROMIZING Study
- A11. Severe, end-stage, irreversible respiratory or cardiac disease

4.2 Screening and Recruitment

We will use a staged recruitment process to identify which eligible patients are enrolled and subsequently randomized in the study if they are not found to be ready for extubation (21), as detailed in the study protocol. The five stages, which are performed to ensure that the patient is ready to tolerate PSV but not ready for extubation at the time of randomization, are as follows: A. Screening Criteria B. Enrolment Criteria and Obtaining Consent C. Pressure Support Criteria and the Pressure Support Tolerance Trial D. Weaning Criteria and the Zero CPAP Trial and the SBT E. Randomization Criteria

4.3 Screening and Recruitment Data

All participating sites are provided detailed screening log templates to track all patients who meet screening inclusion criteria, and record at which of the five stages of recruitment patients are excluded from progressing to the next stage. Screening logs devoid of patient identifiers are sent to the coordinating centre each month. All screening data will be compiled and reported in the CONSORT flow diagram to be included with the publication of the final results. The CONSORT flow diagram will depict (a) the flow of patients through the recruitment process, including the number of patients screened, eligible, enrolled and randomized, and the number of patients excluded and reason for exclusion at each stage; and (b) the flow of patients post randomization (see Figure 1).

Screened # Excluded: # Anticipating palliation # Severe CNS disorder # Neuromuscular disorder # Severe COPD # Broncho-pleural fistula # Tracheostomy present at ICU admission for chronic IMV # Severe, end-stage, irreversible respiratory or cardiac disease · # Enrolment in a confounding study · # Previously randomized in PROMIZING # Unknown # Eligible # Outside 24h randomization window # Extubated # Passed SBT # Plan to extubate within 24hours · # Died # Transferred to a non-participating centre # Patient/SDM declined consent # Unknown # Enrolled # Excluded (Enrolled Not Randomized): # Passed SBT / Extubated • # Patient/SDM declined (after deferred consent) # Patient incapable/no SDM available (after deferred consent) • # Approval withdrawn by physician • # Died # Outside 24h randomization window • # Transferred to another centre # Randomized

Figure 1: CONSORT flow diagram pre-randomization

4.4 Retention, Withdrawal and Follow-up Data

Patients or their SDMs may withdraw consent for ongoing participation in the intervention, or from ongoing data collection, or both. At times, clinicians may choose to deviate from the study intervention or stop the study intervention for safety or other reasons. Finally, patients may be transferred to another hospital, and so may be withdrawn from study intervention for that reason. Part two of the CONSORT diagram will depict the flow of patients post randomization, including number of patients in each arm who started the study intervention, completed the study intervention, were withdrawn from study intervention (and reasons for early withdrawal), the number of patients with complete follow-up data collection to Day 90 or death (and reasons for incomplete follow-up); and number of patients included in the intention-to-treat and per-protocol analyses (see Figure 2).

[figure not shown]

Figure 2: CONSORT flow diagram post-randomization

4.5 Adherence and protocol deviations

Protocol deviations are defined and categorized as minor or major as follows:

Type of Deviation	Category
Patient met criteria for switching from A/C to PAV+, A/C to PSV but not switched	Minor
Patient met extubation criteria but not extubated	Minor
Study timelines not followed	Minor
SBT performed with different respiratory parameters than specified	Minor
Weaning/screening algorithm not followed when patient met weaning criteria	Major
Use of non-protocolized mode	Major

To improve adherence to study interventions, the bedside clinician responsible for adjusting the ventilator (e.g., respiratory therapist, physiotherapist, physician) will complete a daily checklist which will be recorded in the RAVE database. The checklist serves as a reminder to the clinician to follow the study protocol, and also allows us to document protocol adherence. Additionally, use of any non-protocolized mode of ventilation, duration of exposure to non-protocolized mode, and reason for non-protocolized mode is recorded in the database.

Protocol deviation summary reports are presented to the DSMB at regular intervals and include:

- (a) number of deviations of each type that occurred and the category (minor, major)
- (b) number of patients with each type of deviation
- (c) total number of major and minor deviations
- (d) total number of study days
- (e) rate of occurrence, calculated as the number of deviations divided by the total number of study days, expressed as a percentage of the total number of study days, for each type of deviation and in total.

(f) Mode deviations – number of patients who used non-protocolized mode and number of hours spent on non-protocolized mode

Descriptive statistics on use of non-protocolized modes as well as intolerance of PAV+ and PSV (duration in days and percentage of time in study spent on assist/control mode) will be provided

4.6 Analysis Sets

Statistical analysis will be based on intention-to-treat, per protocol analysis. Patients with missing outcome data will be censored at last contact.

4.6.1 Intention To Treat Sample

All analyses will use the intention to treat sample. The intention to treat sample will be comprised of all randomized patients who started the study intervention, irrespective of compliance to their randomized group. Patients will contribute outcome data to the analysis based on the randomized group.

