6.4 Primary Safety Endpoints

Safety analyses will be based on all participants who were randomized to either intervention or control arm, and received either PAV+ or PSV according to study protocol.

Safety will be assessed by evaluating and comparing:

- (i) Frequency and incidence of reported serious adverse events between intervention and control groups.
- (ii) Mortality difference between intervention and control groups

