10.5 Administration of Intervention

Switching ventilator mode to PSV or PAV+ with adjustment of the settings according to the assigned PSV or PAV+ Ventilation Strategy will indicate administering the intervention. The intervention (the PSV or PAV+ Ventilation Strategy) is administered continuously from time of randomization until study completion (study completion occurs at time of successful extubation/successful termination of invasive MV, successful ICU discharge, hospital discharge, death or 90 days post randomization, whichever comes first).

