12.2 Statistical Methods Analysis

Analysis will follow the intention-to-treat principle. Baseline data will be analyzed descriptively (e.g. mean and standard deviation, median and interquartile range, counts and percentages as appropriate). Time to extubation will be summarized by cumulative incidence curves with death treated as a competing risk and compared between groups with the Gray test. The treatment effect will be expressed as a hazard ratio with 95% confidence interval from a multistate generalization of the Cox model. Additionally, a cause-specific Cox model where death is treated as a censoring event will be fit for comparison. Patients with missing outcome data will be censored at last contact. The secondary outcomes of ventilator-free days will be compared between the groups by means of a Wilcoxon test. The treatment effect will be expressed as the difference in median ventilator free days along with a 95% confidence interval obtained by bootstrap methods. The time-to-event outcomes ICU discharge and hospital discharge present the same special challenge as the primary outcome because death is a competing risk. Furthermore, "survivor-only" analyses are an improper subgroup which further complicates interpretation. To mitigate these problems, cumulative incidence curves will be constructed that provide estimates of the outcome of interest, accounting for death. Cause-specific treatment effects will be given as hazard ratios with 95% confidence intervals from Cox models. Time-to-death will be analyzed using standard methods for survival data (Kaplan-Meier curve, log-rank test) and the treatment effect will be expressed as a hazard ratio with 95% confidence interval. Four of the secondary outcomes describe weaning difficulties in various ways. These also suffer from the competing risk of death and other improper subgroup issues. These outcomes will be looked at primarily from a descriptive perspective. The outcome, "requiring A/C" will be compared by a chi-square test (or Fisher's Exact Test) and treatment difference will be expressed as an odds ratio with 95% confidence interval.

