4.6.3 Safety Sample

Safety analysis will include all randomized patients.

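### The set that SAP 4.6.1 calls intention to treat excludes randomized patients who did not start the intervention, and starting is not defined

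*SAP*

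**What the plan says.** SAP 4.6.1 states that every analysis uses the intention-to-treat sample, consisting of "all randomized patients who started the study intervention, irrespective of compliance to their randomized group", analysed by randomized arm. The SAP gives no definition of starting and no cross-reference to one. SAP 4.4 uses the same notion in the post-randomization CONSORT diagram, which counts starters in each arm and, separately, patients in the intention-to-treat analysis.

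The nearest definition is Protocol 10.5, which has two sentences:

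- The first marks administration by "Switching ventilator mode to PSV or PAV+ with adjustment of the settings according to the assigned PSV or PAV+ Ventilation Strategy".
- The second says the intervention "is administered continuously from time of randomization until study completion".

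Other passages on who is analysed carry no starting condition:

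- Protocol 12.2: "Analysis will follow the intention-to-treat principle".
- SAP 3.2, on the primary time-to-event analysis: "no subjects are dropped from the analysis, they are simply censored if necessary".
- SAP 4.6: "Patients with missing outcome data will be censored at last contact".
- SAP 4.6.3: "Safety analysis will include all randomized patients".

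Protocol 6.4 differs from SAP 4.6.3 and limits safety analyses to patients "randomized to either intervention or control arm, and received either PAV+ or PSV according to study protocol".

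**The concern.** A condition met only after allocation can undo the balance that randomization provides. The trial is open label for clinicians and investigators (Protocol 10.3.2), and starting asks for different things in the two arms. PSV can be given on any ventilator that offers it and can begin at the level already in use (Protocol 8.2.1, 8.2.2). PAV+ needs a change of mode on one of two named ventilators (Protocol 8.1.1). If starting means the mode switch, non-starters could therefore fall mainly in the PAV+ arm. If those patients also differ in how fast they come off the ventilator, the primary hazard ratio is biased.

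The sentence also pulls against itself. It keeps patients whatever their compliance, yet never starting is complete non-compliance. A non-starter would count for safety under SAP 4.6.3 but not for efficacy.

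**Working it through.** **1. Who is in the set under each reading**

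| Reading of Protocol 10.5 | Randomized patient never switched to the assigned mode | Effect of the condition |
|---|---|---|
| Mode switch and adjustment (first sentence) | Excluded from the primary analysis | Modified intention to treat |
| From randomization (second sentence) | Included | None; the words are empty |

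Protocol 8.2.2 (PSV may continue at the existing level) and 8.3.4 (the assigned strategy includes assist/control when needed) favour the second reading. SAP 4.4, by counting starters as a separate step, leaves the first open.

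**2. The plan's own figures**

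Required events at HR 1.30 (two-sided 5%, 80% power, 1:1): 4(1.960 + 0.842)² / (ln 1.30)² = 456.1, against 456 stated. Allowing for 5% loss, 529/0.95 = 556.8, so 557 as tabulated; 558 is the next even number (279 per arm). These figures reproduce and are not in dispute.

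**3. Illustration of the bias**

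Inputs from the documents:

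- 279 per arm.
- Liberation hazard from the pooled median of 6.8 days: ln 2/6.8 = 0.1019 per day.
- Follow-up ends at day 90.
- Death hazard 0.0163 per day, solved from the sample-size table. With liberation hazards ln 2/7.70 = 0.0900 and ln 2/5.92 = 0.1171, the mean of 0.0900/(0.0900 + 0.0163) and 0.1171/(0.1171 + 0.0163) is 0.862, and 529 × 0.862 = 456.

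Assumptions, none of them documented: a fraction of patients in both arms has a different liberation hazard. These patients are removed from the PAV+ arm as non-starters, and from PSV at no, half or the same rate. Each setting used 20,000 simulated trials with no true effect. The cause-specific log-rank test stands in for the liberation transition of the multistate Cox model.

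Loss from PAV+ only. The first value in each cell is for non-starters at one third of the others' liberation hazard, the second at one half:

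| PAV+ lost | HR | Type I, cause-specific | Type I, Gray | Favouring PAV+, cause-specific | Favouring PAV+, Gray |
|---|---|---|---|---|---|
| 1% (about 3) | 1.014, 1.010 | 5.4%, 5.1% | 5.3%, 5.0% | 3.7%, 3.2% | 3.2%, 2.9% |
| 2% (about 6) | 1.03, 1.02 | 5.8%, 5.3% | 5.6%, 5.1% | 4.7%, 3.7% | 4.0%, 3.3% |
| 5% (about 14) | 1.07, 1.04 | 11.2%, 7.4% | 7.6%, 5.9% | 10.9%, 6.6% | 6.8%, 4.7% |

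Type I error is two-sided (nominal 5%). The last two columns are false claims in favour of PAV+ (nominal 2.5%). The Monte Carlo standard error is 0.15 points at 5% and 0.22 at 11%.

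Other settings:

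- PSV loses half as many (5% against 2.5%): HR 1.04 to 1.02; type I error 6.6% to 5.6% (Gray 5.6% to 5.4%).
- Loss equal in share and prognosis: HR 1.00; 5.0% to 5.1%.
- Non-starters liberated three times as fast, 2% to 5% lost from PAV+: HR 0.985 to 0.964, against PAV+.
- All randomized patients kept: 4.9% to 5.3% (Gray 4.8% to 5.3%).

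**4. Power cost of keeping everyone**

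True HR 1.30, PAV+ non-starters of average prognosis who get no PAV+ effect, cause-specific test, no loss to follow-up:

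| PAV+ non-starters | All randomized | Started only | Cost (points) |
|---|---|---|---|
| 1% | 81.3% | 82.0% | 0.7 |
| 2% | 80.8% | 82.1% | 1.3 |
| 5% | 77.8% | 81.5% | 3.7 |

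**The case against.** The SAP elsewhere treats failure to switch as non-compliance. SAP 4.5 lists meeting the criteria to leave assist/control without being switched as a minor deviation. SAP 4.6.1 keeps patients regardless of compliance, and SAP 4.6.2 removes withdrawn patients and those with long exposure to other modes only from the per-protocol set. On that view few or no randomized patients would be non-starters. Safeguards point the same way: sites confirm the device (Protocol 4.3), a PAV+ run-in patient comes first (10.1), the pressure support trial must be passed and the physician must agree before randomization (7.3), and the data review is blinded (SAP 2.6). SAP 3.2 concerns missing outcomes, not set membership. *All analyses* is one sentence of 4.6.1, alongside separate per-protocol and safety sets. The 11.2% figure needs about 14 slow patients lost from one arm and none from the other.

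Much of this stands. It makes the mode-switch reading less likely and the probable size small, and SAP 3.2 is supporting context rather than a rival definition. But none of it says who is in the primary set, and the words as written make starting a condition.

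The power runs also ignore the planned 5% loss. With 265 per arm, all-randomized power at 5% non-starters is about 75% instead of 77.8%. The started-only power falls too, so the cost stays at about 4 points.

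**Conclusion.** The concern holds and should be fixed. The primary analysis set is mislabelled, departs from the principle in Protocol 12.2, is narrower than the SAP's safety set if anyone fails to start, and rests on an undefined term. This is an error of definition; it is not evidence that bias will occur. Any effect is negligible at 1% to 2% non-starters and material only if losses are larger, unequal between arms and related to prognosis. It could run in either direction, and it is absent if the intervention counts as started at randomization. Confidence is high on the wording; the magnitude depends entirely on the assumed rate, prognosis and arm split of non-starters.

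**What to change.** In SAP 4.6.1, define the intention-to-treat set as every randomized patient in the allocated arm, whether or not the assigned mode was begun. Missing outcomes are censored as SAP 4.6 already provides. Remove only data for which consent to use was refused, with counts by arm. State that patients randomized in error stay in the set: Protocol 10.7 withdraws them from the study, and retention is the natural reading but is not written. If a started-only set is wanted, call it a modified intention-to-treat sensitivity analysis, define starting by reference to Protocol 10.5, and say which sentence governs. Separately, reconcile the safety population between Protocol 6.4 and SAP 4.6.3.

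The cost is SAP wording, plus whichever document changes for the safety set. No new data are needed: Protocol 2.0 records discharge or death for each randomized patient, and Protocol 9.2 tracks intubations and extubations to day 90 or death. The sample size does not change. The statistical price is the dilution shown above, and there is none if every patient starts.
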